11. RECRUITMENT AND PROCEDURES PREPARATORY TO RESEARCH

Amputees. The Primary Investigator will place Institutional Review Board-approved study advertisements within print and web-based publications that are frequently read by the target population. Additionally, site directors will provide similar Institutional Review Board-approved advertising material to the leaders of local and regional amputee focus/support groups. Individuals who are interested in the study will be directed to contact the study investigators or research coordinators for a thorough description of the study purpose and protocol. Finally, chronic pain physicians will be provided with the IRB-approved advertisements to give to their patients with an amputation and chronic pain.

Individuals interested in the study will contact a research coordinator or investigator by email or telephone (contact information provided in the IRB-approved advertisements). Patients meeting inclusion and exclusion criteria will be presented with the study and provided the IRB-approved ICF and HIPAA consent electronically for their review. Individuals wishing to participate will have the option to (1) print the IRB-approved consent forms, sign the forms, and return them via the postal service; or (2) have UCSD send them the consent forms via a postal service, of which they may then sign and return in pre-addressed and stamped envelopes provided in the original envelope. Following receipt of the signed consent forms, participants will be randomized and sent an active or sham PEMF device by a postal service with instructions to contact the investigative team upon arrival for assistance in applying the device.

Surgical participants. The investigators will need to know in advance which patients would like to participate in order to have a research coordinator present on the day of surgery. The investigators therefore need to contact potential participants prior to their pre-surgery visit and *request a partial waiver of HIPAA authorization for recruitment purposes*. We will scan the upcoming surgery schedule (which we have access to being anesthesiologists—we use this schedule daily for medical purposes), identify patients having the types of surgical procedures specified for this study, look in their electronic records to determine eligibility, and if eligible either call the potential participants ourselves or provide the name and contact information to a research coordinator to contact the potential participants.

1. These procedures are minimal risk to the potential participants as we are anesthesiologists who will be viewing these records even without study participation in preparation for surgery and postoperative analgesia planning. There is no information that an anesthesiologist would not view regardless of the existence of the study.

2. A partial waiver of HIPAA authorization for recruitment purposes would not adversely affect the rights and welfare of the potential participants as we are anesthesiologists who will be viewing these records even without study participation in preparation for surgery and postoperative analgesia

planning. There is no information that an anesthesiologist would not view regardless of the existence of the study.

3. This clinical trial could not be practicably carried out without the partial waiver because many relatively healthy ambulatory patients are not seen in preop clinic; or they are seen just 1-2 days prior to their date of surgery. The investigators will need to know in advance which patients would like to participate in order to have a research coordinator present on the day of surgery.

4. After participants are contacted, if they would like to participate, they will receive written, informed consent using an IRB-approved informed consent form.

These procedures would also include access to PHI:

1. Identifiers will include the potential participant's date of surgery, surgeon, name, phone number, and email address (to send ICF if patient is interested in participation). This information will be recorded in hard-copy format and destroyed using a paper shredder (or in the locked UCSD PHI disposal stations) following contact with the patient. If the patient does not participate, then there will be no record of PHI whatsoever. If the patient does participate, then PHI will be protected as described in #16 below.

2. This clinical trial could not be practicably carried out without the partial waiver because many relatively healthy ambulatory patients are not seen in preop clinic; or they are seen just 1-2 days prior to their date of surgery. We need to schedule a research coordinator to be present for the day of surgery.

3. The privacy risk to individuals whose PHI will be used is minimal since, as anesthesiologists at UCSD caring for ambulatory surgery patients, we use the surgery schedule daily in the normal course of our work caring for patients; and we will not record any PHI other than date of surgery, surgeon, name, contact phone numbers, and email address—and these will be destroyed following use. The anticipated benefit to participants is a chance of improving their postoperative pain control if they are randomized to active stimulation.

4. PHI that will be used includes date of surgery, surgeon, name, contact phone numbers, email address, basic anthropometric data such as height and weight, past medical and surgical history, and the surgical schedule itself. Only coinvestigators will access this PHI, and the only people they might share it with are research coordinators actively participating in this research who understand PHI procedures and to appropriately destroy the hard copy of date/surgeon/name/contact numbers/email address after use.

Patients meeting inclusion and exclusion criteria will be presented with the study, and prospective study participants desiring additional information will be required to give permission for a research coordinator to contact them to adhere to HIPAA requirements. The study protocol will be reviewed with interested prospective participants in detail; and for participants desiring participation, written, informed consent will be obtained prior to any measurements, data collection, and/or interventions. The method of documenting consent will be using written informed consent forms approved by the local Institutional Review Board.

12. INFORMED CONSENT

Amputees. Individuals interested in the study will contact a research coordinator or investigator by email or telephone (contact information provided in the IRB-approved advertisements). Patients meeting inclusion and exclusion criteria will be presented with the study and provided the IRB-approved ICF and HIPAA consent electronically for their review. Individuals wishing to participate will have the option to (1) print the IRB-approved consent forms, sign the forms, and return them via the U.S. Postal Service; or (2) have UCSD send them the consent forms via the U.S. Postal Service, of which they may then sign and return in pre-addressed and stamped envelopes provided in the original envelope. Following receipt of the signed consent forms, participants will be randomized and sent an active or sham PEMF device by U.S. Postal Service with instructions to contact the investigative team upon arrival for assistance in applying the device.

Surgical participants. Candidates who meet inclusion and exclusion criteria and desire study enrollment will be scheduled to arrive the day of surgery 15 minutes earlier than normal to allow for written informed consent and baseline information collection. Written informed consent will be attained prior to any measurements or procedures prior to surgery. When participants present for surgery, research coordinators will provide and attain written informed consent. This will occur in private patient care areas, so that participants may feel comfortable asking questions of the research coordinator.

We do not foresee any issues relevant to the mental capacity of the potential human participants. Written, informed consent will be attained prior to any study procedures or measurements; and participants will not receive procedure-related sedation until following the written, informed consent process is completed. Participants will be provided privacy and time for decision making both in the study description/explanation telephone call to an investigator or research coordinator, as described above; and, the morning of the initial treatment using a private patient care area to again review the study, informed consent form, and answer any remaining questions. As noted previously, participants may speak with an investigator by telephone from initial contact through the morning of treatment; and will have access during and following the treatment(s) with cellular phone and pager numbers provided upon discharge.

This study protocol has follow-up data-collection telephone calls a maximum of 6 months following the initial study treatment (70 days for amputees), so repeated informed consent following the initial consent is unnecessary, as opposed to multi-year, longer-term clinical trials. Surrogate consent will not be accepted; therefore, if human participants cannot provide consent on their own, they will not be offered study enrollment. Consent by an individual's Legally Authorized Representative is unacceptable for study enrollment.

Following informed consent and the signing of the UCSD IRB-approved ICF and HIPAA documents, these documents will be copied, and the copy placed in the patient's medical record. The participant will be provided a copy along with the Participants' Bill of Rights.

13. ALTERNATIVES TO STUDY PARTICIPATION

Patients can decline enrollment. For amputees, their current analgesic regimen will not deviate due to inquiry regarding the study. For surgical patients, they will still receive the standard-of-care postoperative analgesia.

14. POTENTIAL RISKS

There are currently no known medical risks from PEMF, although there is the risk of an allergic reaction to the tape used to hold the device to the skin. There is the risk of loss of confidentiality. The following study procedures will be done to maintain confidentiality of this study: hard copies will be kept in locked medical offices and the locked Investigational Drug Service's files. Any digitized records containing personal health information will be stored as password-protected and encrypted files.

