An analgesic alternative with few associated limitations is **pulsed electromagnetic field (PEMF)** therapy, also called pulsed short-wave therapy, pulsed radiofrequency energy therapy, and radiofrequency nonthermal diathermy.¹ Over the last 7 decades, PEMF has been used to treat acute and chronic pain, decrease inflammation and edema, and hasten wound healing and bone regeneration.¹ Possible mechanisms for the multiple clinical effects of PEMF are multifactorial, complex, and only partially understood.¹ The primary theory involves the promotion of calcium binding to calmodulin which activates endothelial and neuronal nitric oxide synthase isoforms, producing nitric oxide which has anti-inflammatory and analgesic effects, among other consequences

[figure not shown]
such as decreasing edema while increasing blood and lymph flow.¹

[figure not shown]
In 1947, the United States Federal Communications Commission assigned three frequencies for radiofrequency use in medical treatments: 40.68, 13.56 and 27.12 MHz.¹ Within just a few years, the first pulsed electromagnetic field generator was cleared by the United States Food and Drug Administration for use with patients using 27.12 MHz: the Diapulse.^{2,3}. Until relatively recently, available devices consisted of a large signal generator and bulky coil applicator that were not portable and produced significant electromagnetic interference, making them impractical for common use (Figure, right). However, over the past 70 years they have exhibited an extraordinary safety profile: these are noninvasive, nonpharmacologic devices, with no side effects, adverse events, or medication interactions; and the only

contraindications are pregnancy and an implanted pulse generator such as a cardiac pacemaker. Unlike opioids, there is no risk of abuse, dependence, and/or diversion.

More recently, small, simple, lightweight, battery-powered, noninvasive PEMF devices have received FDA clearance for use treating acute and chronic pain, including the ActiPatch and RecoveryRx for amputees and the initial 150 surgical subjects of Phase I (Model 088, BioElectronics, Frederick, Maryland; **Figure, below left**); as well as SofPulse for the subsequent 80 surgical subjects of Phase II (Endonovo Therapeutics, Woodland Hills, California; **Figure below right**). We will be using the devices for FDA-approved indications; in other words, on-label use.

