First described as a therapy to treat postoperative pain in the 1960s,⁴ multiple investigations suggest analgesic benefits following various types of surgical procedures, including breast reduction,⁵ reconstruction,⁶ and augmentation;^{1,7} anterior cruciate ligament reconstruction;⁸ molar extraction;⁹ and cesarean section.¹⁰ Chronic pain conditions have also been treated with PEMF therapy, including knee osteoarthritis and failed back surgery syndrome.^{11,12} However, PEMF has not found widespread use, probably due to the cost and size of the initial large console devices; and later lacking credibility due to scant randomized data. What studies have been published generally involve small sample sizes,^{1,5,7} lack a control group,¹³ lack prospective registration,¹⁰ and/or authors with a significant conflict-of-interest.^{1,8,14-19}

Nevertheless, there appears to be extraordinary unrealized potential for PEMF to treat acute and chronic pain: it can be easily applied in less than one minute by a layperson using tape, induces no side effects (it induces no perceptible sensations at all), is completely noninvasive, is lighter and

thinner than many surgical bandages, may be applied to nearly any part of the body, functions through clothing or bandages, has only two contraindications (pregnancy and an implanted pulse generator), requires no intervention by patient or provider, has a duration of up to 30 days (unlimited duration using serial devices), has not resulted in any adverse events, has no abuse/dependence/diversion potential, and is relatively inexpensive compared to most other analgesics. *Due to its demonstrated benign profile and relatively low cost, PEMF could be applicable to nearly every painful surgical procedure and chronic pain condition, similar to acetaminophen and NSAIDs (only without every 6-hour patient/provider administration and the potential toxicity of acetaminophen and side effects/complications of NSAIDs).*

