Clinical Trials (IMMPACT) consensus statement. All data collection will be through standard UCSD EPIC notes and patient interviews in-person during hospitalization or *via* a telephone call for outpatients. Postoperatively, surgical endpoints will be recorded such as surgical duration. All pain scores will be measured using the Numeric Rating Scale (0: no pain, 10: worst imaginable pain). On Days 35 and 70, amputees will be asked if they would want to continue using the device; and on Day 28 surgical patients will be asked if they would want to use the device if they were to have the same surgery in the future? For Phase II surgical participants, Days 21 and 28 will be excluded due to the shorter treatment period (8 days) of this device relative to that used in Phase I. At all time points for amputees, phantom and residual limb pain will be distinguished and recorded separately.

	Surgical Patients Postoperative Days								Amputees Post-Application Days						
Time Point:															
	1	2	3	7	14	21	28	180	0	2	4	7	21	28	35
Opioid consumption	•	•	•	•	•	•	•	•	•	•	•	•	•	•	•
Average Pain [NRS]	•	•	•	•	•	•	•	•	•	•	•	•	•	•	•
Worst Pain [NRS]	•	•	•	•	•	•	•	•	•	•	•	•	•	•	•
Brief Pain Inventory,				_	_	-	•							•	
Short Form				•	•	•	•		•					•	•
Patient Global												_	•	•	
Impression Change										•	•	•	•	•	•
Sleep disturbances	•	•	•		•	•	•		•	•	•			•	
(#) previous night	•				-					-	-				-
Passive flexion					•										
(knees and hips)															

Summary of post-enrollment assessments (color added for clarity)

Primary end points: This is an exploratory pilot study to assist in planning subsequent definitive trials and we therefore have no data analysis plan. For surgical patients, the two outcomes of primary interest will be (1) the "average" and "worst" pain measured with the Numeric Rating Scale (included in the Brief Pain Inventory pain domain), and (2) opioid consumption within the first 7 postoperative days. For amputees, the outcome measures of primary interest will be (1) the change in "average" residual and phantom limb pain scores between baseline and Day 28 of the initial treatment, as well as (2) the Patient Global Impression of Change on Day 28 of the initial treatment.

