18. RISK/BENEFIT RATIO

There are no known medical risks of PEMF therapy, although there is the risk of allergic reaction from the tape used to secure the device to the skin. With its ease of application, lack of side effects, prolonged duration of action, and simple removal, PEMF therapy has the very real possibility of replacing opioid analgesics—the standard of care for the past 100 years—that would completely revolutionize postoperative analgesia, as we know it.

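### No scheduled contact asks about tape reactions or other adverse events, so the trial cannot estimate a rate and a zero count would not be evidence of absence

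*Combined protocol and SAP*

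**What the plan says.** **The named risk.** Section 14 says there are no known medical risks, although "there is the risk of an allergic reaction to the tape used to hold the device to the skin". Section 18 says the same.

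**The safety premise.** Background describes the devices as "with no side effects, adverse events, or medication interactions" and says the therapy "has not resulted in any adverse events, has no abuse/dependence/diversion potential". It then argues: "Due to its demonstrated benign profile and relatively low cost, PEMF could be applicable to nearly" every painful procedure and chronic pain condition. Section 18 opens its closing argument: "With its ease of application, lack of side effects, prolonged duration of action, and simple removal". The lay summary makes the same claim.

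**What is collected.** Section 9 states: "All data collection will be through standard UCSD EPIC notes and patient interviews in-person during hospitalization or" by telephone for outpatients. The schedule has seven rows: opioid consumption, average pain, worst pain, Brief Pain Inventory, Patient Global Impression of Change, sleep disturbances and passive flexion. The text adds surgical endpoints such as duration, and one question on willingness to continue with the device or use it again.

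**What is analysed.** The statistical text at the end of section 9 defines a pain outcome for Phase II and general test choices. It names no safety outcome. Section 15, on risk management, deals only with pregnancy and implanted pulse generators.

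**The concern.** The one device risk that the protocol names is not solicited at any scheduled contact. Specific Aim 1 is feasibility and optimization of the protocol for later trials, and whether the device can be kept on the skin for its intended period is a feasibility question.

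Several features make silent loss likely:

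- Amputees are "sent an active or sham PEMF device by a postal service with instructions to contact the investigative team upon arrival", may live outside California and place the device themselves, so hospital notes are a weak source for them.
- Surgical participants may take the device off from Day 7 and no reason is recorded. A reaction that ends treatment then looks like preference.
- The willingness question asks for no reason either.

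If the report then says that no events were seen, readers will take it as confirming the safety premise. In these data, no event and not asked would look the same. A tape problem that ought to change the definitive protocol could be missed, and the participants affected might not be identified.

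**Working it through.** The plan gives no event rate, safety margin or safety precision, so there is no figure of its own to reproduce.

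**Step 1: match the named risk to the data items.**

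| Place | Content relevant to skin, tape or adverse events |
|---|---|
| Sections 14 and 18 | Tape allergy named as the only medical risk |
| Section 15, risk management | None; pregnancy and pulse generators only |
| Section 9, schedule (7 rows) | None |
| Section 9, extra questions | Willingness to continue or reuse; no reason asked |
| Section 9, supplemental analgesics | Investigator telephone and pager in business hours; no rule for recording what is reported |
| Section 9, statistical text | None |

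**Step 2: contacts at which a question could be asked.**

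- Phase I surgical: Days 1, 2, 3, 7, 14, 21, 28 and 180, which is 8.
- Phase II surgical: Days 21 and 28 are dropped, so 8 − 2 = 6. Days 1, 2, 3 and 7 fall within the 8-day SofPulse period; Day 14 is the first contact after it.
- Amputees: Days 0, 2, 4, 7, 21, 28 and 35. Day 0 is baseline, so 7 − 1 = 6 per period, or 12 over two periods.

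**Step 3: what a solicited zero would show.** With 0 events in n participants, the one-sided 95% upper limit p solves (1 − p)^n = 0.05, so p = 1 − 0.05^(1/n). The two-sided exact limit uses 0.025. Phase II is 70 in the sample-size text, and 1:1 allocation gives 70/2 = 35 per arm.

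- n = 35: 1 − 0.05^(1/35) = 8.2% (two-sided 10.0%).
- n = 70: 1 − 0.05^(1/70) = 4.2% (two-sided 5.1%).

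Background and the treatment-assignment text give 80 for Phase II instead. On that figure the one-sided limits are 7.2% (n = 40) and 3.7% (n = 80).

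The limit for 35 concerns active participants. The limit for 70 pools active and sham, so it can speak only to tape reactions, not to an effect of the field.

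**Step 4: what an unsolicited zero would show.** The documents give neither a true rate nor the share of reactions that surface unprompted, so both are assumed here. Take a true rate of 5% and a share s surfacing. The chance of recording at least one event is 1 − (1 − 0.05s)^n.

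| Share surfacing | n = 35 | n = 70 |
|---|---|---|
| 10% | 16% | 30% |
| 25% | 36% | 59% |
| 50% | 59% | 83% |
| 100% | 83% | 97% |

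Because s is unknown, a recorded zero cannot be turned into a limit on the true rate.

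**The case against.** The best defence is that safety is a premise here, not an aim. The aims and hypotheses concern feasibility, pain and opioid use. The devices are FDA-cleared and used on-label, and the rationale also rests on ease of use, duration, cost and hoped-for analgesia. Participants are interviewed repeatedly and have an investigator's number, and hospital notes are a data source.

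Much of that stands, and it limits what can be said:

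- A reader might infer that the trial must report zero events, or that it could never contradict the safety premise. The documents do not support this. One volunteered or charted reaction would contradict it, and the table above shows that some recording is quite possible.
- A reader might take the enrolment maximum and claim that a solicited zero would bound the rate at 1 − 0.05^(1/270) = 1.1%. That is not supported. The 270 counts everyone who signs consent, not everyone who wears a device, and it pools sham with active. The Phase II sample size already uses Phase I sham results, so at least some Phase I contacts have passed.
- A reader might assume continuous taped wear at one site for all. The documents specify tape on the wound for Phase I surgical patients and mention it generally elsewhere. Amputees are encouraged to move the devices every two days until they have relief.

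What does not stand is the idea that these routes replace a question. None comes with a definition of what to record or a common denominator. What appears to be section 21 and the consent pages were not available to me, so a general reporting rule there cannot be excluded; it would not put an item in the schedule.

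**Conclusion.** The gap is real and worth closing. The only medical risk named in the protocol is not asked about at any scheduled contact, and no safety analysis is planned, while the rationale relies heavily on an absence of side effects. As written, the trial can pick up an isolated event but cannot estimate a rate, and a zero would not be evidence of absence.

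With the question added, a zero in Phase II would still leave rates up to 8.2% (35 active) or 4.2% (all 70, tape reactions only) compatible with the data. These limits assume 1:1 allocation of 70, every participant wearing a device and answering, and no missed reactions. The primary pain and opioid comparisons are unaffected.

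**What to change.** Add one row to the section 9 schedule: *skin reaction under or around the device or tape (yes/no, severity, action taken), and any other adverse event*. Ask it at every remaining contact after application, up to and including the first contact after device removal, in both groups and in both amputee periods. State that an investigator reviews each positive answer.

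In the statistical text, add a descriptive table of counts per participant by arm with exact confidence intervals, kept separate for Phase I surgical, Phase II surgical and amputee participants. Where contacts have already passed, state that events there were not solicited. Do not report a rate per day of wear unless the date of device removal is also asked, since the schedule does not collect it. Reconcile the 70 and 80 given for Phase II so that the denominator is fixed.

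The cost is a little form entry in calls already planned, one table, and some ordinary postoperative complaints being recorded. Two limits remain:

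- The Phase II sham is a different device (RecoveryRx against SofPulse) with a different stated removal time (Day 30 against Day 8), so it gives only an approximate background rate.
- For a surgical participant who keeps a device to Day 30, the first contact after removal is Day 180, so that answer relies on long recall.
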